17.2 The TiTE-CRM model

A two-parameter Bayesian logistic model with weak priors will be used. The priors are calibrated to ensure the model provides sensible recommendations early in the trial. With this model we can obtain a distribution for the probability of DLT rate given a specific dose d based on all available data. This is a posterior probability distribution for dose d. We write P(T>0.48 | Data, dose = d) to mean the posterior probability that the DLT rate is greater than 48% on dose d, given the data observed so far.

At each dose decision (to assign a dose to the next patient), data for patients who have completed the DLT assessment period or experienced a DLT will contribute full information to this model. Only partial information is known for patients who are currently on trial, within the DLT assessment period, or have stopped treatment in the DLT assessment period for reasons other than a DLT. This partial information contributes to the model, weighted proportionally to the observed portion of their toxicity time window and treating them as not experiencing a DLT.

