6.2 Analysis Methods

Primary analysis

To determine the maximum tolerated dose (MTD), and therefore recommended phase II dose (RPTD), of atovaquone when combined with radical concurrent chemoradiotherapy

All trial patients who received at least one dose of atovaquone will be included in the primary analysis. The same analysis is used during dose escalation as for the final analysis.

The analysis will follow the TiTE-CRM. A two-parameter logistic model will be used to model the relationship between dose and toxicity i.e. the dose toxicity curve (DTC). Dose recommendations following the first two evaluable patients will be made using all current toxicity data as follows:

- Data for patients who have completed the DLT assessment period or experienced a DLT will contribute full information to this model.
- Data for patients who have not completed the DLT assessment period will contribute partial information to the model, weighted proportionally to the observed portion of their time window, and treating them as not experiencing a dose limiting toxicity. The weight function is defined in the equation below as w_i.

There are 4 atovaquone doses which are coded x = 1:4. Assuming dose 1 is the reference dose, d^* , we have treated J patients with dose x_j , j = 1, ..., J, then we model the probability of a DLT occurring using the weighted likelihood given by

$$L(\theta) = \prod_{j=1}^{J} \left[\theta_{x_j} * w_j \right]^{y_j} \left[(1 - \theta_{x_j}) * w_j \right]^{1 - y_j}$$

where

 $y_{j} = \begin{cases} 1 \text{ if dlt occured} \\ 0 \text{ if no DLT} \end{cases}$ $g\left(\theta_{x_{j}}\right) = logit\left(\theta_{x_{j}}\right) = log(\alpha) + \beta log\left(\frac{x_{j}}{d^{*}}\right) \text{ this is the unweighted two-parameter logistic model}$ $w_{j} = \begin{cases} 1 \text{ if } y_{j} = 1 \\ \min\left(1, \frac{u_{j}}{T_{i}}\right) \text{ if } y_{j} = 0 \end{cases}$

 u_j = time patient j has been followed for and T_j = total DLT window for patient j = pre-specified run-in time + 45 days + 84 days (note: as patients are followed up in the trial beyond the DLT observation period, u_j can exceed T_j in which case the weight for patient j in the model will still be 1).

Further detail on the chosen prior distributions for the parameters and simulation results is described in Appendix 1.

See Neuenschwander, Branson and Gsponer (2008) and Cheung YK and Chappell R (2000) for descriptions of the model

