7. VALIDATION OF THE PRIMARY ANALYSIS

Before the trial starts, code for generating dose decisions will be validated by creating a large dataset, and comparing results from analysis using standard logistic regression with the trial code. Although results will not be identical due to the differences between frequentist and Bayesian analyses, with fairly vague priors and a large dataset parameter estimates should be similar. Validation will be stored in the statistical eTMF.

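### As printed in SAP 6.2, the TiTE-CRM weights cancel, so a patient still under observation counts as a completed patient without a DLT

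*SAP*

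**What the plan says.** Both documents intend part-observed patients to count in part. SAP 6.2 says that their data "will contribute partial information to the model, weighted proportionally to the observed portion of their time window". Protocol 17.2 describes them as "weighted proportionally to the observed portion of their toxicity time window and treating them as not experiencing a DLT".

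SAP 6.2 then states that "we model the probability of a DLT occurring using the weighted likelihood given by" the product over patients of

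`[theta*w]^y * [(1 - theta)*w]^(1-y)`

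Here y = 1 for a DLT. The weight is w = 1 for a patient with a DLT, and otherwise min(1, u/T), where u is the follow-up so far. T is the "pre-specified run-in time + 45 days + 84 days". The dose-toxicity model for theta carries no weight: the SAP notes that "this is the unweighted two-parameter logistic model".

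The SAP adds: "The same analysis is used during dose escalation as for the final analysis". SAP 7 plans to validate the code by "comparing results from analysis using standard logistic regression with the trial code".

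**The concern.** The weight is a known number fixed by follow-up time. Multiplying (1 - theta) by a known number rescales the likelihood without changing its shape, so the weight has no effect on the posterior. For it to act, it must change how the DLT-free term varies with theta.

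Handling late toxicity without waiting for the full window is the reason Protocol 17.1 gives for choosing this design. The window is long compared with accrual, so at most interim decisions several patients are only part-observed. If the code follows the printed formula, those patients are over-credited as safe. The DLT rate is then understated, escalation is recommended too early, and the stopping rule fires too late.

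**Working it through.** The plan gives no figure to reproduce here, because the priors and simulations are in SAP Appendix 1, a separate document. The check has an exact part and an illustrative part.

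**1. Algebra (no assumptions).** Taking logs of the printed form:

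`log L = sum[ y*log(theta) + (1-y)*log(1-theta) ] + sum[ log(w) ]`

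The last sum does not involve theta, so for any w > 0 the posterior is the unweighted one. If u = 0, the likelihood is zero at every theta and the posterior is undefined.

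The two outcome terms also add to `theta*w + (1-theta)*w = w` rather than 1. With `1 - w*theta` as the DLT-free term they add to 1.

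**2. Number of patients affected.** T runs from 7 + 45 + 84 = 136 days to 21 + 45 + 84 = 150 days. At one patient per month (Protocol 17.4; 30.4 days), 136/30.4 = 4.5 to 150/30.4 = 4.9 patients are inside their window at a time, out of 20.

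**3. Dose 1 alone, no prior.** Take a 14-day run-in, so T = 143. There is one DLT and four DLT-free patients at 122, 91, 61 and 30 days, so w = 0.85, 0.64, 0.43 and 0.21.
- Printed likelihood divided by unweighted likelihood is 0.0486 at theta = 0.1, 0.3, 0.5 and 0.9. This equals the product of the four weights.
- Maximum-likelihood estimate as printed: 1/5 = 0.200.
- With `1 - w*theta`, the estimate solves `1/theta = sum[ w/(1 - w*theta) ]`, which gives theta = 0.359. Check: 1.23 + 0.83 + 0.50 + 0.23 = 2.79, and 1/0.359 = 2.79.

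**4. Effect on decisions (assumed priors).** These use the SAP's two-parameter model with x = 1 to 4 and T = 143 days. Priors are Normal, written as (mean, SD):
- Set I: log alpha (logit 0.35, 1.5) with log beta (0, 0.7); and log alpha (logit 0.30, 2) with log beta (-0.5, 1).
- Set II: median DLT rate at dose 1 of 25%, 25%, 35% and 40%; SD of log alpha 1, 2, 1 and 1.5; log beta (0, 1), (0, 1), (-0.5, 0.7) and (-1, 1).

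| Data | Quantity | Weight inside | As printed |
|---|---|---|---|
| Dose 1: one completed DLT-free, one DLT, one at w = 0.64. Dose 2: DLT-free at w = 0.43, 0.21, 0.02 (set I) | Posterior mean at dose 2 | 0.45 to 0.52: stay at dose 2 | 0.24 to 0.29: go to dose 3 |
| Dose 1: two DLTs, two DLT-free at w = 0.21 (set I) | P(DLT rate > 0.48) at dose 1 | 0.78 to 0.83: stop | about 0.45: continue |
| Dose 1: two DLTs, DLT-free at 30, 30, 60, 60 days (set II) | P(DLT rate > 0.48) at dose 1 | 0.40 to 0.73: stop under two of four priors | 0.11 to 0.22: never stop |
| Same data (set II) | Posterior mean at dose 1 | 0.44 to 0.63 | 0.30 to 0.35 |

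When every w = 1 (two DLTs in six completed patients), both forms give identical results.

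**5. Whole-trial illustration.** Assumptions: set I priors, one patient a month, DLT times uniform over the window, 500 simulated trials per setting, the plan's escalation and stopping rules applied without committee override, and true DLT rates of 62, 72, 78 and 82%. The trial stops early about four times in five with a working weight and fewer than three times in five as printed. Mean DLTs per trial are about 6 against 9 to 10.

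**6. Final analysis.** Only DLT-free patients who left early then have w < 1. Take dose 1 with 4 patients and 1 DLT, and dose 2 with 16 patients: 6 DLTs, 6 completed DLT-free and 4 withdrawn at w = 0.2. Posterior means at doses 1 to 4 (set I):
- First prior: 0.305, 0.475, 0.578, 0.643 with the weight inside; 0.250, 0.390, 0.486, 0.551 as printed. The selected level moves from 2 to 3.
- Second prior: 0.327, 0.456, 0.536, 0.585 with the weight inside; 0.271, 0.373, 0.444, 0.491 as printed. The closest level moves from 2 to 4, or to 3 if no skipping is applied.

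**7. Validation.** The printed form is the ordinary logistic likelihood, so code written that way will agree with logistic regression on any test data with w > 0. Correct code agrees only when every w = 1. The SAP 7 check therefore cannot expose this error.

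**The case against.** The strongest reply is that this may be only a misprint. The code, Appendix 1 and the Protocol Decision Point Plan are not in the documents. The intended method is described correctly in Protocol 17.2, SAP 6.1 and the SAP 6.2 bullets, and the method's source paper is cited. The printed terms are not a proper Bernoulli model, and the subscripts nearby are inconsistent, so a slip in notation is plausible. This stands: the documents do not show that any dose decision would be wrong. It does not clear the SAP, which is the specification against which the code is written and checked.

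There are also safeguards. SAP 6.4 runs a toxic scenario at each interim that treats patients with insufficient follow-up as DLTs. The Trial Management Group reviews every recommendation and may pause recruitment, and the stop is itself a recommendation to that group. The simulation leaves these out, so it overstates the harm expected in practice. But the toxic scenario is an extreme bound, and neither it nor committee review corrects the primary model or the 0.7 rule.

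A power weight, `(1-theta)^w`, would also make the weight act. Under the second set I prior it would escalate in the first table row, as the printed form does. So the decisions in the table depend on the prior and the form of weight. The `1 - w*theta` form is preferred because it pairs with the printed event term.

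The final-analysis example needs four early withdrawals. With one or two, and the others completing without a DLT, level 3 is selected under both forms once no skipping is applied.

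**Conclusion.** The concern holds for the formula as printed. The weights cancel exactly, under any prior, and this contradicts the partial-information text in both documents. The planned validation would not reveal it.

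The consequences for the trial are conditional on the code following the SAP. If it does, DLT risk is understated at interim decisions: a snapshot can change from staying to escalating, or from stopping to continuing. The sizes are illustrative, because they rest on assumed priors, a 14-day run-in and chosen patient histories. The effect on the final MTD is nil without early DLT-free withdrawals and small with few of them. Because this formula defines the primary analysis and the safety stop, it must be corrected.

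**What to change.** - Replace the SAP 6.2 likelihood with the product of `[w_j*theta_xj]^(y_j) * [1 - w_j*theta_xj]^(1-y_j)`, and make the subscripts on w and T consistently j.
- Confirm that the R and OpenBUGS code uses this form. If the Appendix 1 simulations used the printed form, rerun them.
- Extend the SAP 7 validation with a dataset that includes patients with w < 1, checked against an independent TiTE-CRM calculation. Keep logistic regression as a check for complete data only.
- If any interim recommendation was produced with the printed form, recompute it and give the result to the Trial Management Group.

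The cost is one formula, a code check and one extra validation run, plus a rerun of simulations only if they are affected. No extra patients or data are needed.

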Exploratory Endpoint:	To assess the relationship between plasma atovaquone levels and hypoxia response as measured by FMISO PET-CT and plasma miR-210 level	 Plasma atovaquone concentration Tumour hypoxic volume determined by FMISO PET-CT Plasma miR-210 level 				
Planned enrolment:	20 evaluable participants					
Target Population:	Patients with locally advanced Non-Small Co concurrent chemoradiotherapy					
Investigational Medicinal Products	Name of drug Atovaquone	Formulation, dose, route of administration Suspension, oral, twice daily, dose to be allocated per TiTE-CRM: 450 mg, 600 mg, 675 mg or 750 mg (all doses PO BD)				
	Cisplatin	80 mg/m ² IV on days 1 & 22				
	Vinorelbine	15 mg/m ² IV on days 1, 8, 22 & 29				
Other interventions:						
Study duration:	31 months (start of recruitment to close out)					
Treatment Duration	Up to 9.5 weeks of atovaquone treatment, with concurrent chemoradiotherapy for 6.5 of these weeks					
Follow-up duration	Six months (26-28 weeks) post completion of	of chemoradiotherapy				
End of study	Last Patient Last Visit	· ·				

SUMMARY SCHEDULE OF EVENTS

		ATOVAQUO	NE RUN IN			CHEM	ORADIOTH	ERAPY				FOLLOW UP	
Timing Procedure	Screening ^a	Week -2/-3		Week 1 Day 1 to 7	Week 2	Week 3	Week 4	Week 5	Week 6	Week 7 ^c	Week 10-13 1 month (3-6 wks) post-CRT Day 64 to 91	Week 20-22 3 months (13-15 wks) post-CRT Day 134-154	Week 33-35 6 months (26-28 wks) post-CRT Day 231-245
Informed consent	х	Day -21 to -8	Day -7 10 -1	Day 1 to 7	Day 8 to 14	Day 15 to 21	Day 22 to 28	Day 29 (0 33	Day 30 to 42	Day 45 to 45	Day 04 (0 51	Day 134-134	Day 231-245
Vital signs	х	Xd	Х		Х	Х	Х	Х	Х	Х			
Height	Х												
Weight	Х		Х		Х	Х	Х	Х	Х	Х			
Physical exam	Х	Xd	Х		Х	Х	Х	Х	Х	Х	Х	Х	
ECOG performance status	Х	Xd	Х		Х	Х	Х	Х	Х	Х	Х	Х	
Haematology & biochemistry ^e	Х	Xd	Х		Х	Х	Х	Х	Х	Х			
Pregnancy test (WOCBP only)	Х				Х				Х		Х		
Medical history	Х												
Pulmonary function tests (FEV1 and TLCO)	X ^f												
CT or PET-CT scan ^g	X ^h											Xi	
Atovaquone dispensing		Х		New bottl	e to be disp	ensed as red	quired, each	contains u	p to 21 days	treatment			
Atovaquone treatment completion ^j		XXXXXXX XXXXXXX	XXXXXXX XXXXXXX	XXXXXXX XXXXXXX	XXXXXXX XXXXXXX	XXXXXXX XXXXXXX	XXXXXXX XXXXXXX	XXXXXXX XXXXXXX	XXXXXXX XXXXXXX	XXX XXX			
Radiotherapy	CT simula	tion and RT pl	anning	XXXXX	XXXXX	XXXXX	XXXXX	XXXXX	XXXXX	XXX			
Cisplatin ^k				Х			Х						
Vinorelbine ^l				Х	Х		Х	Х					
Request diagnostic tissue for hypoxia metagene		х											

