2 TRIAL DESIGN

This is a phase I, single arm, open-label trial that will utilise a TiTE-CRM to determine the maximum tolerated dose (MTD) of atovaquone in combination with concurrent CRT in NSCLC. Twenty evaluable participants will be recruited at two centres.

Twice daily oral atovaquone will be added to standard concurrent CRT: 66 Gy in 33 fractions, once daily, 5 days a week (Monday-Friday), with cisplatin (80 mg/m² IV on days 1 and 22 of CRT) and vinorelbine (15 mg/m² IV on days 1, 8, 22 and 29 of CRT). Whilst awaiting CRT to start, patients will receive two weeks (+/- 7 days) of oral atovaquone to ensure steady state is reached (after seven days). Wherever possible, two weeks of atovaquone treatment should be administered prior to CRT, but in appreciation of the difficulty often experienced in radiotherapy scheduling and planning as well as treatment targets, a +/- 7 days window is permitted. In addition, hypoxia biomarker data will be collected at baseline (start of atovaquone run-in) and following two weeks (+/- 7 days) of atovaquone. Atovaquone will then be continued without break for the duration of CRT with the CRT schedule remaining constant for all patients at both centres. Assessment for DLTs will be from the first scheduled dose of atovaquone until three months after completion of CRT. CT scans performed at the three-month follow up visit will be reviewed to collect tumour response data.

The trial will start at the lowest dose of atovaquone (450 mg BD). Two participants will receive this dose and escalation will only be considered when we have 12 weeks of safety data (a high-risk period of developing dose-limiting toxicity, DLT) for at least one participant at this dose level, thus preventing inappropriate early dose escalation. Following this initial safety run in, eligible patients will be continuously recruited and the TiTE-CRM will be used to recommend the dose of atovaquone for each patient, as detailed in section 17.3.

Refer to the schedule of events and flow chart for details of the study visits and procedures.

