2.2 Objectives

The table below shows the full list of trial objectives and corresponding outcome measures. Objectives in grey will be not analysed by trial statisticians within CSM so are not covered by this SAP.

Primary Objective	Endpoints/ Outcome measures	Time point(s) of evaluation of this end point	Analysis population
To determine the maximum tolerated dose (MTD), and therefore recommended phase II dose (RPTD), of atovaquone when combined with radical concurrent chemoradiotherapy in patients with non-small cell lung cancer (NSCLC)	The dose of atovaquone associated with no more than 48% dose limiting toxicity (DLT) rate (target toxicity level)	From week -2/-3 until three months post-completion of CRT	All patients who have received at least one dose of atovaquone
Secondary Objectives			
To assess the safety and	Adverse events graded per	From screening/baseline until	All patients who have
toxicity profile of atovaquone	Common Terminology	six months post completion of	received at least one dose of
in combination with radical	Criteria for Adverse Events	CRT	atovaquone

concurrent chemotherapy for	(CTCAE) v4.03		
NSCLC	. ,		
To confirm feasibility of measuring hypoxia metagene signature using 3'RNA-Seq in diagnostic NSCLC samples	Hypoxia metagene signature from diagnostic tissue using 3'RNA-Seq	At baseline	
To assess pre-treatment agreement of: 1. FMISO PET-CT with plasma miR-210 level 2. FMISO PET-CT with tumour hypoxia gene expression	 Tumour hypoxic volume determined by FMISO PET-CT Plasma miR-210 level Hypoxia metagene signature from diagnostic tissue using 3'RNA-Seq 	Week -2/-3 (prior to atovaquone treatment)	 All patients with outcome measures from both the baseline FMISO PET-CT scan and the baseline blood sample
To assess agreement in changes in FMISO PET-CT and plasma miR-210 level following two weeks (+/- 7 days) of atovaquone	 Tumour hypoxic volume determined by FMISO PET-CT Plasma miR-210 level 	 Week -2/-3 (prior to atovaquone treatment) Following two weeks (+/- 7 days) of atovaquone treatment 	All patients with outcome measures from FMISO PET-CT scans and blood samples taken at both time points
To assess the tumour response rate at three months following treatment	Response to treatment assessed per Response Evaluation Criteria in Solid Tumours (RECIST) V1.1	Three months post completion of CRT	All patients who commence chemoradiotherapy treatment within the study
Exploratory Objectives			

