3. STUDY METHODS

3.1 Trial Design/framework

Arcadian is a single arm, open-label phase I dose escalation trial using the Time-To-Event Continual Reassessment Method (TiTE-CRM) i.e. a model-based approach to determine the maximum tolerated dose (MTD) of atovaquone in combination with concurrent CRT in patients with NSCLC.

Patients will receive an oral suspension of atovaquone twice daily. The four atovaquone dose levels to be assessed in the TiTE-CRM is as follows:

Dose level	
1	450 mg
2	600 mg
3	675 mg
4	750 mg

Patients will receive atovaquone alone for 1 to 3 weeks during a run-in period followed by 6.5 weeks of concurrent chemoradiotherapy (CRT). The 6.5 weeks of CRT consists of two cycles: Cisplatin ($80 \text{ mg/m}^2 \text{ IV}$)

on days 1 & 22, Vinorelbine (15 mg/m² IV) on days 1, 8, 22 & 29 and thoracic radiotherapy: 66 Gy in 33 fractions, once daily, 5 days a week (Monday-Friday). Therefore, the total treatment duration is expected to be up to 9.5 weeks.

Patients will have follow-up visits at approximately 1, 3 and 6 months after completion of CRT.

The TiTE-CRM will take into account toxicity from the start of the atovaquone run-in period to 12 weeks (84 days) after completion of CRT, so the end of the toxicity assessment period will be approximately the time of the 3 months post-CRT visit.

The figure below shows the study schema

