6. ANALYSIS

6.1 Outcome Definitions

Primary outcome

To determine the maximum tolerated dose (MTD), and therefore recommended phase II dose (RPTD), of atovaquone when combined with radical concurrent chemoradiotherapy

The outcome is the occurrence (yes/no) of a DLT within the DLT assessment period. For patients without a DLT, time observed within the DLT assessment period will also be taken into account in the analysis. The total i.e. maximum duration of the DLT assessment period for each patient is the length of the atovaquone run-in period (1-3 weeks) which will be pre-specified before the patient starts treatment, plus the length of CRT treatment (6.5 weeks= 45 days) plus follow-up duration (12 weeks = 84 days). At final analysis, patients without a DLT will have completed the DLT period unless they withdrew early. The MTD will be the dose level with posterior mean DLT rate closest to the target toxicity level of 48% when the dose-toxicity model is updated for the final analysis.

For the definition of a DLT, see Appendix 4.

Secondary outcomes

To assess the safety and toxicity profile of atovaquone in combination with radical concurrent chemotherapy

Adverse events from the first dose of atovaquone to six months post completion of CRT will be presented (see Appendix 3).

To confirm feasibility of measuring hypoxia metagene signature using 3'RNA-Seq in diagnostic NSCLC samples

To assess agreement of FMISO PET-CT with plasma miR-210 level and tumour hypoxia gene expression pretreatment with atovaquone

Hypoxia assessed using the baseline FMISO PET-CT scan will be measured using tumour to blood ratio (TBRvolume) (ml).

Plasma miR-210 level will be derived from the baseline blood sample.

Baseline is at week -2/-3 prior to receiving the first dose of atovaquone.

To assess agreement in changes in FMISO PET-CT and plasma miR-210 level following two weeks (+/- 7 days) of atovaquone

Change in FMISO PET-CT will be the % change between TBRvolume (ml) derived from the baseline and pre-CRT scans.

Change in plasma miR-210 level will be the % change between miR-210 level derived from the baseline and pre-CRT blood samples.

Baseline is at week -2/-3 prior to receiving the first dose of atovaquone and pre-CRT is at week -1 (two weeks (+/- 7 days) after starting atovaquone and prior to receiving any CRT.

To assess the tumour response rate at three months following treatment

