11. APPENDIX 1 (SEPARATE DOCUMENT)

- **12.** APPENDIX 2 (SEPARATE DOCUMENT)
- **13.** APPENDIX 3 (SEPARATE DOCUMENT)
- 14. APPENDIX 4

Definition of a Dose Limiting Toxicity

DLTs are defined as any of the following occurring between the start of trial treatment until three months post CRT, and assessed by the Principal Investigator as possibly, probably or definitely related to atovaquone and/or to chemoradiotherapy. If an event is believed to be possibly, probably or definitely related to treatment with Durvalumab rather than trial IMPs, it may be reported as an SAE rather than a DLT. DLTs must be reported within 24 hours of the site becoming aware.

DLTs will be defined as per NCI CTCAE v4.03 and include:

- Grade \geq 4 absolute neutrophil count (ANC) (<0.5 x 10⁹/L) for >7 days
- Grade ≥3 febrile neutropenia (fever of unknown origin without clinically or microbiologically documented infection) (ANC <1.0 x 10⁹/L, fever ≥38.5°C) lasting >3 days
- Infection (documented clinically or microbiologically) with grade 3 or 4 neutropenia (ANC <1.0 x 10⁹/L)
- Grade ≥3 thrombocytopenia (platelets <25 x 10⁹/L)
- Clinically significant bleeding attributed to grade 3 thrombocytopenia or requiring platelet transfusion
- Grade ≥3 oesophagitis
- Grade ≥3 pneumonitis onset within 3 months of starting radiotherapy
- Grade ≥3 nausea or vomiting not controlled by optimal outpatient anti-emetic treatment for ≥5 days
- Grade ≥3 diarrhoea despite optimal outpatient anti-diarrhoeal medication use

ARCADIAN: A Phase I Trial of the Hypoxia Modifier Atovaquone in Combination with Radical Concurrent Chemoradiotherapy in Locally Advanced Non-Small Cell Lung Cancer. Funded by Cancer Research UK. EudraCT Number: 2019-002097-30. Protocol Number: OCTO_088

- Any toxicity causing a delay of radiotherapy completion by greater than one week
- An elevation of ALT or AST >5 x ULN lasting 8 days or more
- A concurrent elevation of ALT or AST (>3 × ULN) and total bilirubin (>2 × ULN) in whom there is no evidence
 of biliary obstruction or other causes that can reasonably explain the concurrent elevation
- Other grade ≥3 effects thought to be clinically significant and directly related to the combination of atovaquone with chemoradiotherapy

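### The SAP ends the DLT window 84 days after CRT in its model sections but three months after CRT in its endpoint and DLT definitions, with no coding rule for events in between

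*SAP*

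**What the plan says.** Two end points appear for the same period.

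- **84 days after CRT.** SAP 6.2 defines T_j as "total DLT window for patient j = pre-specified run-in time + 45 days + 84 days". SAP 3.1 says the model uses "toxicity from the start of the atovaquone run-in period to 12 weeks (84 days) after completion of CRT", and adds "so the end of the toxicity assessment period will be approximately the time of the 3 months post-CRT visit". SAP 6.1 builds the maximum assessment period from the same parts: a run-in fixed before treatment starts, 45 days of CRT and 84 days of follow-up. It defines the primary outcome as a DLT inside that period, then refers to Appendix 4 for what a DLT is.
- **Three months after CRT.** The primary endpoint row of SAP 2.2 reads "From week -2/-3 until three months post-completion of CRT". Appendix 4 reads "DLTs are defined as any of the following occurring between the start of trial treatment until three months post CRT". Protocol 2 says "Assessment for DLTs will be from the first scheduled dose of atovaquone until three months after completion of CRT", and Protocol 3, 9.1 and 17.1 agree. None of these gives a day count.

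The protocol's schedule of events labels the relevant visit "3 months (13-15 wks) post-CRT", on CRT days 134-154, and marks a DLT assessment there. Protocol 5.4.2 has that visit collect DLTs since the previous assessment. For tumour response, SAP 6.1 also equates three months with 13-15 weeks.

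**The concern.** Whether a patient had a DLT (y_j) is the primary outcome. It feeds every dose recommendation and the final MTD. A related event after day 84 but before three months meets the Appendix 4 definition, yet lies outside the period in which SAP 6.1 counts the outcome. SAP 3.1 says the two dates agree approximately, but not which one governs y_j. SAP 6.1 openly explains its departure from the protocol on response confirmation; it offers nothing similar here.

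There is also a timing problem. The last scheduled DLT visit before the three-month one is 3-6 weeks after CRT. A patient can therefore be treated as fully observed without having attended the final DLT check. SAP 6.2 defines u_j only as time followed, and does not say whether that runs to the extract date or to the last date on which DLT status is known.

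**Working it through.** **1. The plan's own figures.** Thirty-three fractions, Monday to Friday from a Monday, end on day 45. Adding a 14-day run-in gives 14 + 45 = 59 days, the atovaquone duration in Protocol 8.2. Twelve weeks is 84 days. For run-ins of 7, 14 and 21 days, T_j = 136, 143 and 150 days.

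**2. Against the last DLT visit.** T_j ends on CRT day 45 + 84 = 129. The visit window is day 134-154, so T_j ends 5 days before it opens and 25 days before it closes. Measured in weeks (91-105 days), the shortfall is 7-21 days.

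**3. Weights.** At u_j = 143 with a 14-day run-in, the SAP gives weight 1. A 91-day tail gives 143/150 = 0.95 and a 105-day tail gives 143/164 = 0.87. This matters only if the code uses the usual 1 - w × theta form. In the likelihood printed in SAP 6.2, w_j multiplies (1 - theta), so it is a constant and cancels. DLT-free completers have weight 1 at the final analysis under either window.

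**4. Overrun.** If radiotherapy ends 7 days late, T_j is reached 143 - (14 + 52) = 77 days after actual completion, not the 84 in SAP 3.1.

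**5. How many events.** Assume three months is 91 days, a 14-day run-in and uniform onset. Days 85-91 then hold 7/150 = 4.7% of DLTs. Pneumonitis counts only with onset within 3 months of starting radiotherapy, so it cannot fall there. Take it as 40% of DLTs (32 against 48 in Protocol 17.1; 4 against 6 in Protocol 12.5; other types ignored). The share is then 0.0467 × 0.6 = 0.028, or 0.007 at a quarter of the uniform hazard.

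The chance of at least one such event among 20 patients is 1 - (1 - p × s)^20:

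| DLT rate p | s = 0.028 | s = 0.007 |
|---|---|---|
| 0.25 | 0.131 | 0.034 |
| 0.48 | 0.237 | 0.065 |

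Taking three months as 89-92 days, with uniform onset, gives 0.097-0.147 at p = 0.25 and 0.178-0.265 at p = 0.48.

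**6. Effect on the MTD if one is excluded.** A TiTE-CRM was simulated with the two-parameter logistic model, doses coded 1 to 4, N = 20, one patient a month, a 150-day window, target 0.48, the 0.7 stopping rule and no skipping. SAP Appendix 1 was not supplied, so three priors were assumed: log alpha with mean logit 0.30, 0.25 or 0.40 and SD 2, 1.5 or 1; log beta with mean 0, 0 or -0.5 and SD 1, 0.7 or 1. Two runs used 250-300 trials per cell. At the final analysis one random DLT was recoded as none.

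| True DLT rates | Final MTD changed |
|---|---|
| Flat 0.25 | 2.5-7.3% |
| Flat 0.35 | 14.7-21.7% |
| Flat 0.45 | 23.8-31.4% |
| Rising 0.30-0.55 | 23.5-38.7% |
| Rising 0.40-0.65 | 33.5-48.0% |

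Monte Carlo standard errors are up to about 4 points. In the run that recorded direction, every change was upward.

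**7. Combined.**
- Uniform onset, 25% rate: 0.131 × 0.025 to 0.131 × 0.073 = 0.3-1%.
- Uniform onset, 35% rate: chance of an event 1 - (1 - 0.35 × 0.028)^20 = 0.179; times 0.147 to 0.217 = about 3-4%.
- Uniform onset, near target: 0.237 × 0.235 to 0.237 × 0.48 = 6-11%.
- Quarter hazard, all rates: 0.034 × 0.025 to 0.065 × 0.48 = 0.1-3%.

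**The case against.** The protocol never turns three months into days, so doing so is the SAP's job, and three SAP sections give the same answer. SAP 3.1 admits the match is approximate. SAP 6.2 sets y_j to 1 whenever a DLT occurred, with no time limit, and no passage tells the statistician to recode a reported DLT. The Protocol Decision Point Plan, which governs the data used for dose selection, was not supplied. A reader might infer that late DLTs will be dropped and the MTD pushed up. The documents do not establish that; exclusion is one reading of SAP 6.1.

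Late onset is also unlikely to be as common as uniform. The protocol calls the first 12 weeks the high-risk period. Post-CRT day 85 is CRT day 130, which is 101 days after the last vinorelbine dose on day 29. A radiotherapy-delay DLT cannot arise once radiotherapy is over, and events attributed to durvalumab may be reported as SAEs instead. The 6-11% figure is therefore an upper case. The TMG reviews each interim recommendation as well.

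A fixed T_j is workable while actual dates are unknown. A reader might conclude that actual dates should simply replace planned ones. That would shorten the window for someone who stops radiotherapy early: stopping on CRT day 20 gives 14 + 20 + 91 = 125 days and weight 1 at day 125, against 125/143 = 0.87 under the SAP.

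What remains is that the SAP gives its primary outcome two end points, and no document supplied says which decides the coding of an event between them.

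**Conclusion.** The inconsistency is real and lies on the face of the SAP; it does not depend on the weights or the priors. Its likely effect is small: about 0.1-3% of trials with a changed MTD at a quarter of the uniform late hazard, and 6-11% only with near-target DLT rates and uniform onset. Those figures assume that late events would be excluded, that three months is 91 days, that pneumonitis makes up 40% of DLTs, and the three priors above. The direction seen, towards a higher dose, is a reason to settle the rule before such an event occurs. The weight effect is conditional on the code using 1 - w × theta. This is a clarification worth making, between minor and should-fix, held with moderate confidence.

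**What to change.** - State one day count for the end of the window that agrees with the protocol's three months post-CRT. Use it in SAP 2.2, 3.1, 6.1, 6.2 and Appendix 4, for both y_j and T_j.
- State that any event meeting Appendix 4 within that window is coded y_j = 1.
- State that u_j runs to the last date on which DLT status is known in the data extract, and check this against the Protocol Decision Point Plan.
- Keep the planned run-in and 45 days of CRT in T_j as a minimum. Lengthen T_j when the actual run-in or CRT overruns; do not shorten it for patients who stop CRT early.

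The cost is SAP wording, minor programming, and slightly lower interim weights for some patients.
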